6.2.2.3. Analysis of Change from Baseline in CD4+ T-cell counts

The changes from baseline in CD4+ cell count and the absolute values of CD4 cell counts at Weeks 26, 52 and other post-baseline visits will be summarized by treatment group for FAS, Week 26 PP analysis set and Week 52 PP analysis set using descriptive statistics.

The differences in changes from baseline in CD4+ T-cell count between the two treatment groups (Treatment Group 1 versus Treatment Group 3) and the associated 95% CIs and p-values will be constructed using analysis of covariance (ANCOVA) models in the FAS analysis set, including baseline CD4+ T-cell count as a covariate and treatment as a fixed-effect in the models. A secondary analysis based on the Week 26 PP and Week 52 PP analysis sets will also be performed.

The mean and 95% CI of change from baseline in CD4+ cell count over time by treatment groups will be plotted for the FAS.

6.3. Other Efficacy Endpoints

6.3.1. Definition of the Other Efficacy Endpoints

- Proportion of participants with HIV-1 RNA $<$ 50 copies/mL by visit.
- The change from baseline in CD4+ percentage (%) at Weeks 26 and 52.

6.3.2. Analysis of the Other Efficacy Endpoints

6.3.2.1. Analysis of Proportion of Participants with HIV-1 RNA < 50 copies/mL by visit (Missing = Failure and Missing = Excluded Approaches).

All collected data in the randomized phase will be used for this analysis. Number and percentage of participants with HIV-1 RNA < 50 copies/mL by visit will be analyzed using the following 2 imputation methods for missing HIV-1 RNA values:

- Missing = Failure (M = F):

In this approach, missing data will be treated as virologic failure and summarized into the “missing” category (see list of HIV-RNA categories below). Results will be summarized by treatment group for all visits up to Week 26.

- Missing = Excluded (M = E):

In this approach, missing data will be excluded from the computation of the percentages (ie, missing data points will be excluded from both the numerator and denominator in the computation). The denominator for percentages at a visit is the number of participants in the FAS with nonmissing HIV-1 RNA value at that visit.

For both M = F and M = E analyses, the number and percentage of participants with HIV-1 RNA in the following categories will be summarized based on the FAS:

- < 50 copies/mL
 - < 20 copies/mL
 - < 20 copies/mL Not Detectable
 - < 20 copies/mL Detectable
 - 20 to < 50 copies/mL
- 50 to < 200 copies/mL
- 200 to < 400 copies/mL
- 400 to < 1000 copies/mL
- ≥ 1000 copies/mL
- Missing (only applicable to M = F analysis)

The proportion of participants with HIV-1 RNA < 50 copies/mL as defined by the 2 different missing data imputation methods will be analyzed using the same statistical method applied to the primary endpoint. In addition, the 95% CI of the proportion of participants with HIV-1 RNA < 50 copies/mL within each treatment will be provided using the Clopper-Pearson Exact method.

For the M = F analysis, results will be summarized by treatment group for all visits up to Week 52. For the M = E analysis, results will be summarized by treatment group for all visits with available data.

For the M = F analysis, the proportion of participants with HIV-1 RNA < 50 copies/mL will be plotted by treatment group for all visits up to Week 52 using the FAS.

For the M = E analysis, the proportion of participants with HIV-1 RNA < 50 copies/mL will be plotted by treatment group for all available visits using the FAS.

6.3.2.2. Analysis of Change from Baseline in CD4 Percentage

The change from baseline in CD4 percentage (%) will be based on the FAS and analyzed up to the visits with available data, similarly to the change from baseline in CD4 cell count.

6.3.3. Efficacy Subgroup Analysis

The efficacy analysis by subgroup will be conducted by assessing the proportion of participants with HIV-1 RNA \geq 50 copies/mL, or < 50 copies/mL at Weeks 26 and 52 determined by the US FDA-defined snapshot algorithm within each subgroup specified in Section 3.4 based on the FAS.

Results will be descriptive and the associated 95% CIs will be constructed using the Clopper-Pearson Exact method.

6.4. Changes from Protocol-Specified Efficacy Analyses

No change from protocol-specified efficacy analysis is planned.

7. SAFETY ANALYSES

Analysis of safety data will be conducted on the Safety Analysis Set for randomized phase, unless otherwise specified in the following sections.

For randomized phase, the treatment-emergent (TE) period is defined as follows:

For treatment group 1 participants who receive any long acting LEN, TAB and ZAB, the TE period is the time period from the first dose date of study drug in the randomized phase up to and including the last study date (randomized phase) (Section 3.8.1). For participants who do not receive any injection or infusion but only receive oral LEN and permanently discontinued study drug, the TE period is the time period from the first dose date of study drug in the randomized phase up to and including 60 days after the last dose of the oral LEN.

For treatment group 3 participants, the TE period is the time period from the first dose date of study drug for the randomized phase up to and including study day 1(extension phase) for participants who enter extension phase or up to and including 30 days after the last dose date of randomized phase for the participants who do not enter extension phase.

In general, safety data during the TE period will be summarized, unless otherwise specified.

7.1. Adverse Events

7.1.1. Adverse Event Dictionary

Clinical and laboratory AEs will be coded using the current version of the Medical Dictionary for Regulatory Activities (MedDRA). System organ class (SOC), high-level group term (HLGT), high-level term (HLT), preferred term (PT), and lower-level term (LLT) will be provided in the AE dataset.

7.1.2. Adverse Event Severity

Adverse events are graded by the investigator as Grade 1, 2, 3, 4, or 5 according to toxicity criteria specified in the protocol. The severity grade of events for which the investigator did not record severity will be categorized as “missing” for tabular summaries and data listings. The missing category will be listed last in summary presentation.

7.1.3. Relationship of Adverse Events to Study Drug

Related AEs are those for which the investigator selected “Related” on the AE eCRF to the question of “Related to Study Treatment.” Relatedness will always default to the investigator’s choice, not that of the medical monitor. Events for which the investigator did not record relationship to study drug will be considered related to study drug for summary purposes. However, by-participant data listings will show the relationship as missing.

7.1.4. Serious Adverse Events

Serious adverse events (SAEs) will be identified and captured as SAEs if the AEs met the definitions of SAEs that were specified in the study protocol. SAEs captured and stored in the clinical database will be reconciled with the SAE database from the Gilead Global Patient Safety (GLPS) Department before data finalization.

7.1.5. Treatment-Emergent Adverse Events

7.1.5.1. Definition of Treatment-Emergent Adverse Events

Treatment-emergent AEs (TEAEs) in the randomized phase are defined as 1 or both of the following:

- Any AEs leading to premature discontinuation of study drug during randomized phase, or
- Any AEs that start during the TE period (Section 7)

Treatment-emergent AEs (TEAEs) in extension phase are defined as 1 or both of the following:

- Any AEs leading to premature discontinuation of study drug during extension phase, or
- Any AEs that start on or after study day 1 (extension phase) (section 3.8.1)

7.1.5.2. Incomplete Dates

If the onset date of the AE is incomplete and the AE stop date is not prior to the first dose date of study drug, then the month and year (or year alone if month is not recorded) of onset determine whether an AE is treatment emergent. The event is considered treatment emergent as follows:

- Participants who receive any injection or infusion drug: the AE onset date is the same as or after the month and year (or year) of the first dose date of study drug
- Participants who do not receive any injection or infusion drug:
 - The AE onset is the same as or after the month and year (or year) of the first dose date of study drug, and
 - The AE onset date is the same as or before the month and year (or year) of the last day of the TE period

An AE with completely missing onset and stop dates, or with the onset date missing and a stop date later than the first dose date of study drug, will be considered to be treatment emergent. In addition, an AE with the onset date missing and incomplete stop date with the same or later month and year (or year alone if month is not recorded) as the first dose date of study drug will be considered treatment emergent.

When calculating the duration of event or time to onset, the following imputation rule will be used:

Missing start month/day: Jan 1/first day of the month will be used unless this is before the start date of study drug; in this case the study drug start date will be used;

Missing stop month/day: Dec 31/last day of the month will be used, unless this is after the last study date; in this case the last study date will be used.

7.1.6. Summaries of Adverse Events and Deaths

Treatment-emergent AEs will be summarized based on the Safety Analysis Set.

7.1.6.1. Summaries of AE incidence

A brief, high-level summary of the number and percentage of participants who experienced at least 1 TEAE in the categories described below will be provided by treatment group. All deaths observed will also be included in this summary.

The number and percentage of participants who experienced at least 1 TEAE will be provided and summarized by SOC, HLT (if applicable), PT and treatment group or by PT only and treatment group for the following AE categories:

- TEAEs
- TEAEs with Grade 3 or higher
- TEAEs with Grade 2 or higher
- TE treatment-related AEs
- TE treatment-related AEs with Grade 3 or higher
- TE treatment-related AEs with Grade 2 or higher
- TE SAEs
- TE treatment-related SAEs
- TEAEs leading to death (by SOC and PT only)
- TEAEs leading to premature discontinuation of study drug
- TEAEs leading to premature discontinuation of study

Multiple events will be counted only once per participant in each summary. For summaries by SOC and PT, AEs will be summarized and listed first in alphabetical order of SOC and then by PT in descending order of total frequency within each SOC. For summaries by PT only, AEs will be summarized and listed by PT in descending order of total frequency. For summaries by severity grade, the most severe grade will be used for those AEs that occurred more than once in an individual participant.

In addition, data listings will be provided for the following:

- All AEs
- All SAEs
- All Deaths
- All AEs with severity of Grade 3 or higher
- All AEs leading to discontinuation of study drug
- All AEs leading to discontinuation of study

For each listing, whether the event is treatment emergent will be indicated.

7.1.7. Additional Analysis of Adverse Events

7.1.7.1. Study Drug Related Injection Site Reactions and Infusion Related Reactions

For Treatment Group 1, additional analysis of AEs will be performed for injection site reaction (ISR) (i.e., defined by high level term (HLT) of "Injection site reactions") and infusion related reaction (IRR), (ie, AE with "Yes" answer to "Is this part of an infusion-related reaction?" in AE CRF). Summaries will be provided for each SC injection visit (e.g, Day 1 SC, Week 26, and Week 52) and the overall.

- Number of participants received any injection or infusion
- Number and percentage of participants with study drug related ISRs or IRRs
- Number and percentage of participants with study drug related ISRs or IRRs by grade
- Number and percentage of participants with study drug related ISRs or IRRs by PT

The denominator for the percentage calculation for the by visit summary and the overall summary will be based on the number of participants received at least one injection or infusion in Safety Analysis Set.

Duration of the ISR will also be calculated and summarized. Duration of a given ISR event is defined as the ISR stop date minus the ISR onset date plus 1 day. For ISRs with ongoing stop date, stop date will be imputed as last study date or data cut date, whichever is the earliest. Duration of ISR events in days will be summarized by PT and overall using descriptive statistics. Duration of a given IRR event is defined as the IRR stop date minus the IRR onset date plus 1 day, and duration of IRR will be listed also.

By-participant listings for ISRs or IRRs will be provided.

7.1.7.2. Study Drug Related Injection Site Induration and Nodules

For Treatment Group 1, percentage of ongoing and resolved study drug related “Injection Site Induration” (one of preferred terms of ISR) will be summarized at both participant-level and event-level. Summaries will be provided for each SC injection visit (e.g, Day 1 SC, Week 26, and Week 52) and the overall at participant and event level.

For the participant-level summary, if a participant had more than one injection site indurations, the participant will be counted in the “Ongoing” category unless all study drug related injection site induration events have been resolved.

For the event-level summary, duration of the resolved events will be summarized using descriptive statistics.

Study drug related “Injection Site Nodules” (another preferred term of ISR) will be summarized in the same manner as defined for study drug related injection site induration.

A by participant listing for study drug related injection site induration and nodules and the corresponding duration will be provided.

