7.7. Toxicity Management

All clinical and clinically significant laboratory toxicities will be managed according to uniform guidelines detailed in Appendix 11.5, and as outlined below:

Grade 3 or 4 clinically significant laboratory abnormalities should be confirmed by repeat testing as soon as possible, and preferably within 3 calendar days after receipt of the original test results.

Treatment-emergent toxicities will be noted by the investigator and brought to the attention of the medical monitor, and the appropriate course of action will be discussed and decided. Whether or not considered treatment-related, all participants experiencing AEs must be monitored periodically until symptoms subside, any abnormal laboratory values have resolved or returned to baseline levels or they are considered irreversible, or until there is a satisfactory explanation for the changes observed.

Any questions regarding toxicity management should be directed to the medical monitor.

All clinical sequelae in relation to SSRs will be reported as AEs or SAEs at the same time using the AE eCRF and/or the SAE report form. Details of the symptoms and signs, clinical management, and outcome will be reported, when available.

For management of infusion-related reactions, please see Section 5.3.1.

7.7.1. Management of ISRs of Grade 3 or Higher or Persisting for More Than 26 Weeks

In clinical studies of SC LEN, Grade 3 or higher AEs of ISRs were uncommon. Some participants experienced AEs of injection site nodule and induration, which decreased in size over 6 months or longer. For AEs of ISRs related to SC LEN injection that are Grade 3 or higher or persisting for more than 26 weeks, particularly nodule and/or induration, the investigator must contact the medical monitor and discuss the appropriate next steps for further assessment and management of ISR. ISRs that last longer than 26 weeks will be followed clinically until resolution or study completion, and the time of resolution will be documented. Photographic documentation of ISRs that meet above criteria is recommended but not mandatory. If obtained, documentation will be shared with the sponsor and study team.

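### The two injection-site reaction duration summaries use inconsistent rules and neither censors ongoing events, so the duration of long-lasting reactions can be understated

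*SAP*

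**What the plan says.** SAP 7.1.7.1 defines the measure: "Duration of a given ISR event is defined as the ISR stop date minus the ISR onset date plus 1 day". For events without an end it adds: "For ISRs with ongoing stop date, stop date will be imputed as last study date or data cut date, whichever is the earliest". The durations then go into an ordinary summary: "Duration of ISR events in days will be summarized by PT and overall using descriptive statistics".

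SAP 7.1.7.2 takes up injection site induration, which it names as a preferred term of ISR. The percentages ongoing and resolved "will be summarized at both participant-level and event-level", by injection visit (Day 1, Week 26, Week 52) and overall. A participant counts as ongoing unless every such event has resolved. On duration it says: "For the event-level summary, duration of the resolved events will be summarized using descriptive statistics". Nodules "will be summarized in the same manner as defined for study drug related injection site induration". Durations are also listed by participant.

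Protocol 7.7.1 says that in earlier studies some participants had nodules and induration "which decreased in size over 6 months or longer". It has ISRs lasting more than 26 weeks followed until they resolve or the study is completed, with the time of resolution recorded.

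**The concern.** The duration of an event that is still present at the analysis is right-censored: only a lower bound is known. Section 7.1.7.1 enters that lower bound as if it were the duration. Section 7.1.7.2 leaves the event out of the duration statistic, which favours events short enough to have ended within follow-up. For long-lasting events both rules pull toward short durations, and they can give different figures for the same nodules in one report.

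How long a nodule or induration lasts is a natural tolerability question for an injection given every 26 weeks, and the protocol uses 26 weeks as its persistence threshold. Follow-up also differs by injection, so a comparison of durations across injections would partly be a comparison of follow-up.

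**Working it through.** The documents give no ISR duration, resolution rate or data cut date, so there is no plan figure to reproduce. The check asks what each rule returns when the true duration is known.

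**Follow-up.** SAP 2.1.1 places the analysis after all participants have completed Week 52 or discontinued. Minimum follow-up for completers is therefore 52 − 0 = 52 weeks after the Day 1 injection, 52 − 26 = 26 weeks (182 days) after the Week 26 injection, and 52 − 52 = 0 weeks after the Week 52 injection. Participants enrolled earlier have more.

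**Closed form.** Assume exponential durations with true median m, so the rate is r = ln 2 / m and the true mean is 1/r. Take follow-up F = 182 days for every event.

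- Share ongoing: exp(−rF).
- Resolved-only median: the t that solves 1 − exp(−rt) = ½[1 − exp(−rF)].
- Ended-at-cut mean: (1/r)[1 − exp(−rF)].
- Ended-at-cut median: the smaller of m and F.

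For m = 182: 1/r = 182/0.6931 = 262.6 and exp(−rF) = 0.5. The resolved-only median is −ln(0.75) × 262.6 = 75.5 days, and the ended-at-cut mean is 262.6 × 0.5 = 131.3 days. The other rows follow in the same way:

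| True median (days) | Share ongoing | Resolved-only median | Ended-at-cut median | Ended-at-cut mean | True mean |
|---|---|---|---|---|---|
| 125 | 36% | 69 | 125 | 115 | 180 |
| 182 | 50% | 76 | 182 | 131 | 263 |
| 300 | 66% | 82 | 182 | 149 | 433 |

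The resolved-only median moves only from 69 to 82 days while the true median goes from 125 to 300. In that range it says more about follow-up than about the reactions.

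**Sensitivity to shape and injection.** Durations were simulated as Weibull with shape 1 (exponential) and shape 2, 200,000 events per scenario. Follow-up was 52 weeks after Day 1, 26 weeks after Week 26 and, by assumption, 0 to 26 weeks after Week 52. Results in weeks, lower to higher across the two shapes:

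| True median | Injection | Ongoing | Resolved-only median | Ended-at-cut median |
|---|---|---|---|---|
| 4 | Day 1 or Week 26 | at most 1% | 3.9–4.0 | 4.0 |
| 26 | Day 1 | 6–25% | 17.6–24.9 | 26 |
| 26 | Week 26 | 50% | 10.9–16.7 | 26 |
| 26 | Week 52 | 72–81% | about 6–12 | about 6–12 |
| 52 | Week 26 | 70–84% | 12–18 | 26 |

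At a true median of 26 weeks, the ended-at-cut mean is 2–25% low after Day 1. After Week 26 it is 18.8 against a true 37.5 (shape 1), or 21.1 against 27.7 (shape 2). With 26 weeks of follow-up neither rule can show a duration above 26 weeks.

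**After the fix.** With ongoing events censored, Kaplan-Meier gives about 26 weeks or 'not reached' for the Week 26 injection when the true median is 26. Pooled over three injections with an assumed 26 weeks of accrual, Kaplan-Meier returns 26.0, against 16.9–19.8 (ended at cut) and 14.3–22.1 (resolved only).

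**The case against.** The strongest reply is that ongoing events are not hidden. Section 7.1.7.2 reports the percentages ongoing and resolved, by visit and overall, labels its duration as that of resolved events, and provides listings. That stands: events are dropped from the duration statistic, not from the report. But a percentage ongoing, without the follow-up behind it, does not give a duration.

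Four further points stand and limit the concern.

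- The ended-at-cut median equals the true median whenever every event's follow-up reaches it. In the closed form it is exact at 125 and 182 days. A reader might infer that every figure under 7.1.7.1 is too low; that holds for the mean and the longer quantiles, not for this median.
- A reader might infer from Protocol 7.7.1 that nodules typically last 6 months or more. The text speaks of some participants and of shrinkage. It gives no typical duration, so every true median above is an assumption.
- 182 days is the minimum for Week 26 events, not the usual value, because earlier-enrolled participants have longer follow-up.
- These are descriptive summaries in one arm at the Week 52 interim analysis. They bear on no efficacy endpoint, comparison or decision rule, and a final analysis follows.

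SAP Appendix 3 item 6 mentions a Kaplan-Meier figure. That is a general display convention; the SAP specifies no time-to-resolution analysis of ISRs.

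**Conclusion.** The inconsistency is real. Induration and nodules get one duration summary with ongoing events ended artificially and another with them left out, and neither censors them. For reactions lasting about 6 months or more after the Week 26 or Week 52 injection, the understatement can be large. After the Week 26 injection, the resolved-only median is 36–58% low at a true median of 26 weeks and 65–77% low at 52 weeks. The exponential case at 182 days gives 76 against 182 days for the resolved-only median, and 131 against 263 days for the ended-at-cut mean. After Day 1, at a true median of 26 weeks, the shortfall runs from near nil to about a third. Short ISRs are barely affected.

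These sizes rest on assumed distributions and minimum follow-up. The documents do not support the flat statement that ISRs as a whole will look much shorter than they are. Because this is a descriptive safety summary, the change is one to consider, not a necessity.

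**What to change.** Use one rule in both sections: Kaplan-Meier time to resolution for induration, nodules and ISRs overall, with ongoing events censored at the earlier of last study date and data cut.

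- Present it by preferred term and, where numbers allow, by injection visit. Give the number ongoing, the median or 'not reached', and the proportion still present at 26 weeks. Give 52 weeks only where follow-up allows, which will generally exclude the Week 26 and Week 52 injections.
- State that events within a participant are correlated, or add a participant-level version.
- State which stop dates apply to participants who enter the extension. SAP Section 3 assigns AEs from the first extension dose onward to the extension phase, yet 7.1.7 lists the Week 52 injection as a summary visit.
- Keep the resolved-only durations as a labelled supplement or listing.

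The cost is one extra table from dates that the planned summaries already use. With about 50 treated participants some strata will be sparse, and reported durations will be longer.
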